**Specific Aims:**

The primary objective of this study is to identify whether a smaller dose of spinal bupivacaine combined with fentanyl reduces the incidence of maternal hypotension and fetal bradycardia in laboring parturients receiving combined spinal-epidural analgesia.

The secondary objective is to evaluate the adequacy of pain relief with the reduced dose of spinal anesthetic.

Outcomes to be measured include:

1. Maternal hypotension. Defined as 20% decrease in systolic blood pressure (when compared with baseline) or a systolic blood pressure less than 100 mm Hg.
2. Fetal bradycardia. Defined as a fall in heart rate to less than 110 bpm, or a prolonged deceleration defined as a fall in heart rate to less than 110 bpm lasting more than 2 minutes.
3. The need to administer ephedrine, phenylephrine, terbutaline, or nitroglycerin to support blood pressure and/or improve the fetal heart rate following the spinal dose
4. Adequacy and duration of pain relief following the spinal using a numeric pain rating scale from zero to ten.
5. Mode of Delivery- Normal spontaneous vaginal delivery, vacuum assisted/forceps, or caesarean section

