Power analysis: As this is an exploratory but well controlled study, we will set the power at 0.9 and alpha at 0.05. 9 per group are required with an incidence fetal bradycardia/maternal hypotension of 7%; thus we will study 30 per group = 180 subjects. Accounting for dropouts and incomplete data, we seek to consent 200 patients. Published data estimates that the incidence of maternal hypotension after spinal bupivacaine is 10-15% at the higher 2.5 mg dose and likely reduced to 3-5% at the lower doses. The incidence of fetal bradycardia is less well studied but is estimated to occur in 3-7% of parturients after the higher 2.5mg bupivacaine dose. The occurrence of fetal bradycardia at lower doses of bupivacaine is not well studied but our prediction is that it will be reduced.

F tests- ANOVA: Repeated measures, between factors	Repetitions = 4
Analysis: A priori: Compute required sample size	Corr among rep measures = 0.5
Input: Effect size f = 1.2472191	Output: Noncentrality parameter λ =
a err prob = 0.05	Critical F = 5.143253
Power (1-err prob) = 0.90	22.399999
Number of groups = 3	

Numerator df = 2.000000  
Denominator df = 6.000000  
Sample size = 9  
Actual power = 0.903879  
Total sample size = 180

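### The 7% incidence offered as the basis for the sample size names no arm and no defined event, does not enter the printed calculation, and leaves the 90% power claim unsupported for both hypotension and fetal bradycardia

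*Combined protocol and SAP*

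**What the plan says.** Specific Aims puts two events in the primary objective, asking whether a smaller dose "reduces the incidence of maternal hypotension and fetal bradycardia in laboring parturients". It then lists them as outcomes 1 and 2, each with its own definition: "Maternal hypotension. Defined as 20% decrease in systolic blood pressure (when compared with baseline", with an alternative absolute threshold, and "Fetal bradycardia. Defined as a fall in heart rate to less than 110 bpm", with an alternative for prolonged deceleration. No combined outcome is defined anywhere.

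The Power analysis paragraph under Statistical Analysis sets power at 0.9 and alpha at 0.05, then says "9 per group are required with an incidence fetal bradycardia/maternal hypotension of 7" per cent. From this it moves to 30 per group, equated with 180 subjects, and a consent target of 200. The same paragraph gives the "incidence of maternal hypotension after spinal bupivacaine is 10-15% at the higher 2.5 mg dose and likely reduced to 3-5% at the lower doses", and fetal bradycardia as "estimated to occur in 3-7% of parturients after the higher 2.5mg bupivacaine dose". It gives no bradycardia figure for the lower doses, only a prediction that the rate will fall.

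The output printed below it is for a repeated-measures ANOVA, between factors. Its inputs are f = 1.2472191, alpha 0.05, power 0.90, 3 groups, 4 repetitions and correlation 0.5. Its results are a sample size of 9, denominator df 6 and actual power 0.903879.

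**The concern.** The prose presents one incidence as the basis for the size, but that incidence has no arm, no dose and no defined event. The slash could mean each event separately, a woman with either, or a woman with both, and these have different expected rates. Set beside the rates in the same paragraph, 7% is below the whole hypotension range at 2.5 mg.

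What is at stake is the 90% power claim. If the stated incidence is neither interpretable nor used, nothing in the document shows that the planned size can answer the primary question for either event. A null result could then be read as evidence of no dose effect when the trial had little chance of showing one.

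**Working it through.** **1. The plan's own figure.** For the between-groups test in a repeated-measures ANOVA with m repetitions and correlation ρ, λ = f² × N × m / [1 + (m − 1)ρ], with df 2 and N − 3.

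- f² = 1.2472191² = 1.5556, m = 4, ρ = 0.5, so the divisor is 1 + 3 × 0.5 = 2.5.
- N = 9 in total: λ = 1.5556 × 9 × 4 / 2.5 = 22.40, critical F(2, 6) = 5.1433, power = 0.9039. This matches the printout.
- N = 27 (9 per group): λ = 67.2, denominator df 24, power above 0.9999. This does not match.

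The 9 is therefore a total, 3 per group. The 7% is not among the printed inputs, and f is given without derivation.

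**2. What 7% could be at 2.5 mg.** Inputs from the Power analysis paragraph: hypotension H = 10-15%, bradycardia B = 3-7%.

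- Either event: max(H, B) ≤ P(either) ≤ H + B. Lowest: max(10, 3) = 10%. Highest: 15 + 7 = 22%. If independent: 1 − 0.90 × 0.97 = 12.7% to 1 − 0.85 × 0.93 = 21.0%.
- Both events: P(both) ≤ min(H, B), so at most 7%.
- Hypotension alone: 10-15%. Bradycardia alone: 3-7%.

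So 7% is excluded for hypotension and for either event at this dose. It is the top of the bradycardia range and the ceiling for both events together.

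**3. What 7% could be across arms** (equal arms).

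- Hypotension: (10 + 3 + 3)/3 = 5.3% to (15 + 5 + 5)/3 = 8.3%.
- Either event, for example 12.7%, 4%, 4% (the lower-dose figure is assumed): 20.7/3 = 6.9%.

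An average of 7% is arithmetically possible, but the text does not say that this is meant.

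**4. Power for the incidence outcomes.** The document names no test for event incidence, so a three-group Pearson chi-square with 2 df at alpha 0.05 is assumed. The test rejects when Σ(xᵢ − x̄)² / [x̄(1 − x̄/n)] exceeds 5.991, where xᵢ is the event count in arm i, x̄ the mean count and n the arm size. Power is the total binomial probability of the rejecting outcomes. Both readings of the size are shown: 180/3 = 60 per arm, and 30 per arm (30 × 3 = 90).

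| Outcome, rates at 2.5 / 1.66 / 1.25 mg | 60 per arm | 30 per arm |
|---|---|---|
| Hypotension 10 / 5 / 5% | 18% | 9% |
| Hypotension 12.5 / 4 / 4% | 44% | 21% |
| Hypotension 15 / 3 / 3% | 74% | 40% |
| Bradycardia 7 / 2 / 2% (lower doses assumed) | 27% | 13% |
| Bradycardia 7 / 3.5 / 3.5% (assumed) | 13% | 7% |
| Bradycardia 3 / 1 / 1% (assumed) | 10% | 4% |

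The hypotension rows span the paragraph's own ranges; no row reaches 90%.

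**5. For scale.** Comparing two arms on hypotension with 90% power (two-sided 0.05, no continuity correction, no multiplicity adjustment) needs 118 per group for 15% v 3% and 582 per group for 10% v 5%.

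**The case against.** The strongest reply is that 7% is unlabelled rather than wrong. The paragraph ties it to no arm. It is an allowed bradycardia rate at 2.5 mg, and a joined event can have a pooled rate like any other, as the 6.9% example shows. All of this stands. A reader might infer that 7% is numerically impossible; the documents do not support that. It is excluded only for hypotension and for either event at 2.5 mg.

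A reader might also infer that the plan has switched to a composite endpoint. No composite is defined, Specific Aims and the data-collection list keep the events apart, and the slash may be shorthand for the pair. What remains is that the wording does not settle it.

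A third reply is that 7% does not drive the printed size, so correcting it alone changes nothing there. That is true, and it cuts both ways: the prose says the size is required with that incidence, yet the calculation never uses it.

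Finally, one might argue that the choice between hypotension and an either-event outcome changes power several-fold. It does not: the hypotension range alone (18-74% at 60 per arm) covers what plausible either-event rates give (about 46% at 12.7 / 4 / 4% to about two thirds at 21 / 7 / 7%).

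**Conclusion.** The concern holds in a limited form. The stated incidence is undefined as to event and arm, and it plays no part in the printed calculation. The 90% power belongs to an ANOVA with 9 women in total and an unexplained effect size; it is not power to compare event rates. On the protocol's own hypotension rates the delivered power is 18-74% at 60 per arm and about 9-40% at 30. For bradycardia it is about 10-27% and 4-13%.

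These figures assume a three-group chi-square, equal arms, the same rate in both lower-dose arms and, for bradycardia, lower-dose rates that the document does not supply. The hypotension shortfall does not depend on that last assumption.

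**What to change.** In the Power analysis paragraph:

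- Delete the sentence that derives 9 per group from a slash-joined 7%, and withdraw the 0.9 power claim for both outcomes, not for bradycardia alone.
- State the rates by outcome: hypotension 10-15% at 2.5 mg v 3-5% at the lower doses; bradycardia 3-7% at 2.5 mg v a lower rate explicitly marked as assumed.
- State that the two outcomes are scored and reported separately, as Specific Aims defines them. Label any either-event outcome as supportive.
- Reconcile 30 per group (90 in total) with 180 subjects (60 per group).
- Name the test for event incidence and restate the power it delivers for each outcome at the reconciled size. Report bradycardia as an estimate with a confidence interval.

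The cost is rewriting one paragraph; no extra patients or data are needed. The downside is that the stated power becomes much less favourable. The rewording makes the claim accurate; it does not bring the trial to 90% power.

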## Experimental Design and Method:

The clinical trial will take place between January 1, 2014 to January 1, 2015 in the Labor and Delivery unit at the ***Roosevelt site of Mount-Sinai-Roosevelt Hospital Center.***

This randomized prospective double-blinded study is designed to investigate the development of maternal hypotension and fetal bradycardia in patients receiving CSE for labor analgesia. ***The target population are laboring patient admitted to the Labor and delivery unit. Any patient requesting an epidural for labor will be a potential candidate for this study.*** Discussion regarding the patient's participation in the trial will occur when she requests labor analgesia, as this is the customary first point of contact with the anesthesiology team. After informed consent and discussion of the technique for combined spinal-epidural, patients will be blindly randomized to one of three groups. ***The randomization will be done by blindly choosing one of these papers from the envelope, which will assign you to one of the three groups.***

These groups relate to the dose of bupivacaine that will be administered intrathecally during placement of the spinal anesthetic. Syringes will be prepared in advance by pharmacy containing one of the three doses of bupivacaine being identified only by a syringe number. Twenty micrograms of fentanyl is routinely administered in combination with bupivacaine in the spinal. ***The total amount in the syringe will be the same in the group, by adding saline when needed. Pharmacy will be providing us with prepared syringes containing either one of the 3 dosages of Bupivacaine for the spinal part of the combined spinal epidural (CSE). The syringes will be labeled with a number, and only pharmacy will know what concentration of bupivacaine is in the syringe. We will be given this information of what was in the syringe once final data are collected for the patients included in the study. The syringe will be prepared with a sterile technique, and the content will be ready to use as is by the anesthesia team providing the CSE.***

Group 1: 2.5 mg plain bupivacaine + 20 mcg fentanyl

Group 2: 1.66 mg plain bupivacaine + 20 mcg fentanyl

Group 3: 1.25 mg plain bupivacaine + 20mcg fentanyl

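### The planned sample size contradicts itself: 30 per group in a three-group trial is 90, not 180, and the 9 per group cited in support is a program total

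*Combined protocol and SAP*

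**What the plan says.** The Experimental Design and Method section states that "patients will be blindly randomized to one of three groups" and lists three groups, one per bupivacaine dose. The power program's input agrees: "Number of groups = 3".

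The power analysis paragraph under Statistical Analysis then gives these sample-size figures:

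- a requirement: "9 per group are required with an incidence fetal bradycardia/maternal hypotension of 7"%;
- the planned size: "thus we will study 30 per group = 180 subjects";
- a recruitment target: "Accounting for dropouts and incomplete data, we seek to consent 200 patients";
- below the program output, the total again: "Total sample size = 180".

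The program output, for a repeated-measures ANOVA on the between-groups factor, gives a sample size of 9 with "Denominator df = 6.000000" and "Actual power = 0.903879".

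**The concern.** Thirty per group gives 180 only with six groups. The documents describe three, and mention no strata, second factor or other structure that would supply six. So either the per-group figure or the total is wrong.

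This sentence is the only place where the plan gives an intended group size. Pharmacy prepares syringes of three doses in advance, and allocation is by papers drawn from an envelope. Both steps would ordinarily be set up from a per-group number. Someone working from 30 would set up a trial half the size of the one implied by the total. The primary objective concerns maternal hypotension and fetal bradycardia, which the plan itself expects to be uncommon, so halving the size matters.

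The supporting figure is also doubtful. A denominator of 6 degrees of freedom with three groups points to 9 subjects altogether, not 9 in each group.

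**Working it through.** **1. Per-group size against total.** Inputs: 3 groups (design section and program input), 30 per group, 180 in total. Equal allocation is assumed; no ratio is stated, but a single per-group figure implies it.

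- 3 × 30 = 90, not 180.
- 180 / 3 = 60 per group.
- 180 / 30 = 6 groups, which the plan does not have.

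**2. Which figure fits the rest of the paragraph.** Input: 200 consents. The plan gives no dropout rate, so the allowance is back-calculated.

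- From 180: 1 − 180/200 = 10% loss.
- From 90: 1 − 90/200 = 55% loss.

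**3. The program output.** Inputs as printed: f = 1.2472191, m = 4 repetitions, correlation ρ = 0.5, k = 3 groups, alpha 0.05. For this test

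λ = f² × N × m / (1 + (m − 1)ρ), with df k − 1 and N − k.

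Here f² = 1.55556 and m / (1 + 3 × 0.5) = 4 / 2.5 = 1.6.

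| Total N | λ | df | Critical F | Power |
|---|---|---|---|---|
| 8 | 19.911 | 2, 5 | 5.786 | 0.825 |
| **9** | **22.399999** | **2, 6** | **5.143253** | **0.903879** |
| 27 (9 per group) | 67.200 | 2, 24 | 3.403 | >0.9999 |

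N = 9 in total reproduces every printed value, and 9 per group reproduces none of them. The program therefore returned 9 subjects, or 3 per group. Neither 30 per group nor 180 comes out of this calculation, and the plan does not explain the step from 9 to 30.

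**4. What the factor of two means.** Rates are from the power analysis paragraph: hypotension 10–15% at 2.5 mg and 3–5% at the lower doses; fetal bradycardia 3–7% at 2.5 mg.

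| Quantity | 30 per group | 60 per group |
|---|---|---|
| Hypotension events, 2.5 mg arm (n × 0.10 to n × 0.15) | 3.0–4.5 | 6–9 |
| Hypotension events, all arms (n × 0.16 to n × 0.25) | 4.8–7.5 | 9.6–15.0 |
| Bradycardia events, 2.5 mg arm (n × 0.03 to n × 0.07) | 0.9–2.1 | 1.8–4.2 |
| Chance of no bradycardia in that arm, at 3% (0.97ⁿ) | 40% | 16% |
| Same, at 7% (0.93ⁿ) | 11% | 1% |
| 95% CI half-width, hypotension, 2.5 mg vs one lower dose (percentage points) | 12.3–15.0 | 8.7–10.6 |

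The all-arms multipliers are 0.10 + 0.03 + 0.03 = 0.16 and 0.15 + 0.05 + 0.05 = 0.25. The half-width is 1.96 × √(p₁q₁/n + p₂q₂/n), running from 10% vs 3% to 15% vs 5%.

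As illustration only, a 2-df chi-square test with one shared rate at both lower doses has simulated power of 9–40% with 30 per group and 18–74% with 60. At 12.5/4/4% the figures are 21% and 44%. The plan does not name this test.

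**The case against.** The strongest objection concerns direction. The documents prove that 30 and 180 disagree, not that 30 is the slip. The second statement of 180 sits beneath output that belongs to N = 9, so it may only repeat the sentence above it. The 10% allowance is inferred; it shows that 200 was probably built on 180, but multiplying 30 wrongly would have led to the same 200. Sixty is never given as a group size. This stands as a caution: 60 is the reading that fits best, and only the sponsor can settle it.

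Second, the consequence is conditional. The explicit recruitment instruction is 200 consents, and nothing says enrolment stops on a per-group count. That is fair. Halving the trial is a risk of the wording, not a certainty. It does not rescue a sample-size statement that cannot be followed as written.

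Third, the 9 per group slip changes no planned number, and relabelling it would leave a sentence saying that 3 per group suffice at a 7% incidence. This also stands, and makes removal the better of the two remedies.

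Fourth, the interval widths and chi-square power use large-sample methods on small counts. With 30 per group, a lower-dose arm expects only 0.9–1.5 hypotension events. These figures should be read as orders of magnitude. The event counts and zero-event probabilities do not depend on such approximations, and the conclusion does not rest on the power figures.

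**Conclusion.** The concern holds. The stated per-group size and total are incompatible in a three-group trial and differ by a factor of two: 30 per group (90) against 60 per group (180). The contradiction needs only the number of groups, which two places in the document confirm, and equal allocation. That 60 was intended is an inference from the repeated total and the consent target, and needs confirmation.

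The 9 per group figure is also wrong. The printed output reproduces exactly with 9 in total, so the text presents a requirement three times the one returned (27 against 9).

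Because the planned sample size is a figure the trial relies on, the sentence must be corrected. Correcting it does not justify the 0.90 power: neither size follows from the printed calculation.

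**What to change.** - Ask the sponsor which figure was intended. If it was the total, state 60 per group and 180 in total, and leave the target of 200 consents as it is.
- If 30 per group was intended, change the total to 90 in both places and the consent target to match: 90 / 0.90 = 100 at the same 10% allowance.
- State the dropout allowance explicitly, so that the consent target can be checked.
- Preferably remove the 9 per group statement together with the ANOVA calculation. If the calculation stays for now, describe its result as 9 in total (3 per group).

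The cost is one confirmation from the sponsor and a few figures in one paragraph. Keeping the total of 180 adds no patients.

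### The stated 90% power belongs to a repeated-measures ANOVA on nine women in total; at the protocol's own hypotension rates, a three-group chi-square with 60 per group has about 18-74% power

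*Combined protocol and SAP*

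**What the plan says.** Under Specific Aims, the primary objective is whether a smaller spinal dose "reduces the incidence of maternal hypotension and fetal bradycardia in laboring parturients". Both outcomes are defined there by thresholds, so each woman either has the event or does not.

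The power analysis paragraph under Statistical Analysis calls the study exploratory but well controlled, and in the same sentence says "we will set the power at 0.9 and alpha at 0.05". It continues "9 per group are required with an incidence fetal bradycardia/maternal hypotension of 7" per cent, and then "thus we will study 30 per group = 180 subjects". Consent is sought from 200 to allow for losses. Hypotension is expected in "10-15% at the higher 2.5 mg dose and likely reduced to 3-5% at the lower doses". Fetal bradycardia is put at 3-7% at 2.5 mg, with no figure for the lower doses.

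The software output below that paragraph is headed "F tests- ANOVA: Repeated measures, between factors". It lists "Input: Effect size f = 1.2472191", four repetitions, a correlation of 0.5, three groups, "Denominator df = 6.000000", a sample size of 9 and an actual power of 0.903879. It then gives a total sample size of 180. No test for comparing proportions is named anywhere in the document.

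**The concern.** The calculation and the objective concern different quantities. The ANOVA compares group means of a continuous variable averaged over four measurements. The objective compares proportions. The plan names no variable measured at four times: pain is scored at three, and blood pressure is taken far more often. The single 7% incidence is not an input to the output, and one incidence cannot define a difference between groups.

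The sample size statements also conflict with each other. A denominator df of 6 with three groups means nine subjects in all, but the text reads it as nine per group. Thirty in each of three groups makes 90, not 180.

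At stake is how the result will be read. If the trial is described as having 90% power and finds no significant difference, readers may conclude that dose does not affect hypotension or bradycardia. If the real power is much lower, that conclusion is unwarranted.

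**Working it through.** **1. Reproduce the printed output.** Inputs from the output: f = 1.2472191, m = 4 repetitions, ρ = 0.5, 3 groups, α = 0.05.

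λ = f² × N × m / (1 + (m − 1)ρ), with df = (2, N − 3)

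- N = 9 in total: λ = 1.5556 × 9 × 4 / 2.5 = 22.400; critical F(2, 6) = 5.14325; power = 0.903879. All three match the document.
- N = 27 (nine per group): λ = 67.2; critical F(2, 24) = 3.403; power above 0.999. This does not match.

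The printed power is therefore for nine women in total, three per group.

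**2. Compare the effect size with the protocol's own rates.** For proportions, Cohen's f = SD(p) / √(p̄(1 − p̄)), taken over the three equal groups.

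| Hypotension rates (2.5 / 1.66 / 1.25 mg) | p̄ | f | 1.2472 / f |
|---|---|---|---|
| 10 / 5 / 5% | 6.67% | 0.094 | about 13 |
| 12.5 / 4 / 4% (midpoints, my choice) | 6.83% | 0.159 | about 8 |
| 15 / 3 / 3% | 7.00% | 0.222 | about 6 |

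The f used is roughly 6 to 13 times what the protocol expects.

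**3. Power for the yes/no outcomes.** Assumptions: equal allocation, 180 read as 60 per group, two-sided α = 0.05 for each event with no multiplicity adjustment. Power is by exact enumeration of all three-group tables. The pooled test compares 2.5 mg with both lower doses together.

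| Rates | Chi-square, 3 groups | Trend over dose | Pooled chi-square | Pooled Fisher |
|---|---|---|---|---|
| Hypotension 10/5/5 | 17.9% | 23.7% | 26.0% | 21.2% |
| Hypotension 12.5/4/4 | 44.3% | 52.5% | 56.4% | 50.4% |
| Hypotension 15/3/3 | 74.1% | 80.0% | 83.0% | 79.1% |
| Bradycardia 7/3.5/3.5 (halving assumed) | 12.6% | 18.1% | 19.2% | 16.3% |
| Bradycardia 3/1.5/1.5 (halving assumed) | 6.6% | 8.1% | 13.1% | 8.5% |

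Cross-check: the noncentral chi-square approximation with λ = 180 × f² gives 19% at 10/5/5 and 76% at 15/3/3, close to the exact values. Simulation with unequal lower-dose rates (3% and 5%) falls inside the range.

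**4. If 30 per group is meant.** Chi-square power for hypotension is 20.6% at 12.5/4/4, range 8.8% to 39.6%. For bradycardia at 7/3.5/3.5 it is 7.0%.

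**5. Size needed for 90% power, hypotension.** By simulation:
- 12.5/4/4: about 180 per group (chi-square), 162 (trend) or 148 (pooled).
- 15/3/3: about 92, 82 or 77.

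At 10/5/5 the noncentral chi-square approximation gives about 473 per group for the three-group chi-square.

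**The case against.** - **The study calls itself exploratory.** This does not help, because the same sentence sets power at 0.9.
- **180 is far above 9, so there is margin.** The 9 has no bearing on proportions, and 180 still falls short in step 3.
- **Sidedness is not stated and the aim is directional.** A one-sided pooled test at 15/3/3 has 89.1% power with 60 per group, and 91.4% if all 200 consented women (about 66 per group) were analysed. That is the most favourable set of rates. At 12.5/4/4 with 60 per group the same test has 66.7%, and the extra 20 women are there to cover losses.
- **The 7% may refer to either event combined.** If 15% and 7% are added with no overlap, 22% against 5/5% gives 87% (chi-square), 90% (trend) or 93% (pooled). So 90% can be reached on this reading. However, Specific Aims defines no composite, a 7% composite does not fit with 10-15% for hypotension alone, and 5% allows almost nothing for bradycardia at the lower doses. With 22/8.5/8.5% power is 60-71%.
- **The bradycardia figures depend on an assumed halving.** This objection stands. A larger fall raises the power: 7/1/1% gives 46% with the three-group chi-square and 61% pooled. No bradycardia power can be fixed until a lower-dose rate is stated.

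**Conclusion.** The concern holds. The 0.90 is the power of a different test, on an unnamed continuous variable, with nine women in total and an effect size unrelated to the protocol's rates. It is wrong as a statement about the primary objective.

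At 60 per group, no two-sided test of hypotension tried here reaches 90% at the protocol's own rates; the best case is 83% (pooled chi-square, 15/3/3). This rests on equal allocation, on reading 180 as 60 per group (the more generous of the two readings), and on the full 0.05 being spent on each event. Sharing alpha between the two events would lower the power further. The bradycardia figures are illustrative only.

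**What to change.** Rewrite the power analysis paragraph:

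1. Delete the ANOVA output and the 0.90 claim, and the statement that nine per group are required.
2. Reconcile 30 per group with 180, and state the number per group.
3. State whether hypotension, bradycardia or a defined composite is primary, and how alpha is shared if there is more than one.
4. Name one primary test for the per-woman events and its sidedness, and quote the power of that same test. The two-sided options at 60 per group are in step 3 of the working. The three-group chi-square makes no use of dose order. The trend test does, and gives 53% at 12.5/4/4 (24-80%). The pooled chi-square gives 56% (26-83%) but no separate answer for each lower dose. If an exact test is chosen, quote its own lower power (pooled Fisher 50%, 21-79%).
5. State the assumed lower-dose bradycardia rate with a range, labelled as an assumption.
6. Report risk differences with 95% confidence intervals, and say that a non-significant result is not evidence of no effect.

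The cost is one rewritten paragraph and a less favourable stated power. Extra patients are needed only if the sponsor keeps the 90% target.
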